6.1.2 Family History/Age at Onset Assessment/Demographics/Study Partner Information

Family history, specifics of family mutation and age at onset assessment as well as demographic and study partner information will be collected during the CRI screening visit (CRI Screen) or treatment screening period (V1) and confirmed at the CRI Entry or baseline visit (V2). See the *Global Manual of Operations* for details of the age at onset assessment and the required family/pedigree genetic mutation documentation.

6.1.3 Medical/Treatment History, Concomitant Medications, Adverse Event Assessment

At all visits, the participant's clinically significant medical history and names and dosages of all medications will be reviewed. Medications taken within 90 days of any screening visit (CRI Screen/V1) will be obtained at the respective visit (CRI Screen/V1) and reviewed at all subsequent visits. Prior medications taken for dementia and any interval changes in medications including over-the-counter medications should be reviewed at every visit. Use of alcohol, caffeine, and abused substances will be reviewed. Interval history and presence and severity of any adverse events will be documented at follow-up visits.

6.1.4 Clinical Assessment

The full clinical assessment is performed by interviewing the study partner and participant at CRI Entry, baseline (V2), and annual visits for both the CRI and treatment periods; for certain populations, the MMSE is to be completed at the 26 week (approx. 6-month) visit between annual visits (timing for specific study populations is provided in the CRI appendix and each drug-specific appendix). Audio recordings of some assessments will be made for quality control; see *Global Manual of Operations* for details. The following test instruments will be administered:

- a. Clinical Dementia Rating (CDR) and calculation of CDR-SB. CDR-SB includes supplemental boxes for language and behavior.
- b. Assessment of clinical diagnosis (Clinician judgment of symptoms)
NOTE: For each participant, the CDR and assessment of clinical diagnosis should be administered by the same experienced clinician at all visits. Whenever possible, the CDR rater should not be involved in other assessments (e.g., MMSE, FAS, GDS, NPI-Q) or in cognitive testing.
- c. Geriatric Depression Scale (GDS)
- d. Functional Assessment Scale (FAS)
- e. Neuropsychiatric Inventory Questionnaire (NPI-Q)
- f. Mini-Mental State Examination (MMSE)

See the *Global Manual of Operations* for details of administration. All staff administering these batteries must be appropriately trained and certified as specified in the *Global Manual of Operations* for the trial.

6.1.5 Physical and Neurological Examination

Physical examination will include skin, head, eyes, ears, nose and throat, respiratory, cardiovascular, abdomen, lymph nodes and musculoskeletal.

A complete neurological examination will also be completed. At visits after CRI entry and/or baseline, any clinically significant changes will be documented and reported.

6.1.6 Vital Signs

During the CRI period, blood pressure, heart rate, respiratory rate, temperature, and weight will be collected at CRI Screen, CRI Entry, and annual visits. Height will be collected at CRI entry and annual visits only.

During the treatment period, blood pressure, heart rate, respiratory rate and temperature will be collected at all visits. Height will be measured at least at baseline (V2), and weight will be measured approximately every 3 months starting at baseline unless otherwise specified in the drug-specific appendix. Weight collected between on-site annual visits may be obtained at a medical facility where participants receive safety MRIs or at the participants' homes.

6.1.7 Electrocardiogram

A standard 12-lead ECG will be performed at the indicated visits based on the CRI period and study drug arm requirements. Refer to each drug-specific appendix for more details.

For the CRI period and gantenerumab OLE, ECGs will be performed and read locally by a qualified physician or cardiologist, and investigators are to ensure no evidence of exclusionary findings.

For other treatment arms, a central read vendor will be utilized. The site principal investigator or designated sub-investigator will be responsible for initial read on ECGs done at baseline (V2). In the event that the central read becomes available after study drug is administered and is exclusionary when the local read was not, the site principal investigator or designated sub-investigator, in consultation with the PAL, Medical Director or designee, will decide if the participant should continue in the study. A discrepancy between the local and central read will not be considered a protocol deviation. When there are differences in ECG interpretation between the investigator and the cardiologist at the central ECG laboratory, the investigator's interpretation will be used for study entry and immediate participant management.

Interpretations from the cardiologist at the central ECG laboratory will be used for data analysis and report writing purposes. ECGs done at visits conducted at sites other than the DIAN-TU site may be done at a sponsor approved local site or by a home health nurse. These will be sent to the central reader and will also be available to the host DIAN-TU site.

6.1.8 C-SSRS

The Columbia Suicide Severity Rating Scale (C-SSRS) will be administered at screening (V1) and baseline (V2), and generally approximately every 3 months thereafter for the first 2 years during the treatment period. The C-SSRS may then be administered less frequently, i.e. approximately every 6 months and/or annually for the remaining duration of the study. Refer to the drug-specific appendices for exact timing.

The C-SSRS will be administered at CRI Entry during the CRI period.

6.1.9 Genetic Testing

Determination of mutation status for DIAD causing variants (*APP*, *PSEN1*, *PSEN2*) and *APOE* genotype will be performed in the trial-designated CLIA-approved laboratory at CRI Screen visit or screening (V1). The results from the CLIA-approved laboratory will be used for purposes of the DIAN-TU-001 study (e.g., for randomization) but will not be communicated to the participants or sites. Participants who wish to learn their DIAD mutation status, or when required for study entry, will be referred for genetic counseling and testing.

Blood samples for provenance⁵ testing will be obtained at the CRI Entry visit or baseline visit. Genetic testing results from the CRI period may be used to fulfill the required testing at screening and baseline for the treatment period.

For an open-label extension (OLE) period, if the participant does not know their genetic status and is interested in joining the OLE, the clinical genetic report generated from the study's genetic testing at trial entry may be provided to the appropriate party managing the genetic counseling and disclosure for the participant, i.e., the PI or genetic counselor.

In addition to mutation status, genetic factors that may affect or explain responses to treatments will be explored. Specifically, the genetic profile (both RNA and DNA) of cells found in both CSF and blood samples collected during the trial will be studied. These data will not inform participant care but have the potential to inform researchers of the mechanisms of the study drug on important aspects of Alzheimer's disease biology.

6.1.10 Clinical Laboratory Tests

Clinical laboratory testing includes hematology with differential, chemistry (including liver enzyme tests and electrolytes), and urinalysis (macro and micro). In addition, TSH, vitamin B₁₂ levels, hemoglobin A1c, PT, PTT, and INR are obtained only at the CRI Screen and screening visit (V1). Drug-specific appendices may require additional testing; refer to the drug-specific appendices and central laboratory manual for a complete list of analytes to be tested for each drug arm.

Clinical laboratory samples will be obtained and sent to a central laboratory for analysis. During the CRI period, laboratory values obtained at CRI Screen must be reviewed prior to completion of CRI Entry. Laboratory values obtained at screening (V1) must be reviewed prior to completion of baseline (V2) biomarker measures (PET imaging, vMRI, LP-CSF). The site principal investigator or designated sub-investigator must review all laboratory results and document any clinically meaningful abnormal results as an AE; see Section 7.1.1 for criteria to determine if an abnormal result is clinically meaningful. If results from the central laboratory for coagulation studies are unavailable at the baseline visit, results from a local laboratory may be used to confirm that a participant is able to continue with baseline visit procedures, including randomization and study drug dosing. Central lab samples should be sent and used for study reporting purposes. Any clinically meaningful abnormal result that occurs during the study (after screening) should be repeated within an appropriate time frame (as determined by the site principal investigator or designated sub-investigator and/or PAL, Medical Director or designee).

Refer to Section 7 (Safety and Adverse Events) for further details regarding adverse events.

⁵ Provenance testing is performed for quality assurance purposes to ensure that genetic blood sample obtained at baseline visit is from the same individual as the sample obtained at the screening visit.

Pregnancy testing – people of childbearing potential only

During the CRI period, serum pregnancy testing will be performed at the CRI Screen visit and urine pregnancy testing will be performed at annual visits for women scheduled for [¹⁸F]MK-6240 PET scans. During the treatment period, serum pregnancy testing will be performed at screening (V1) and the safety follow-up visit; and urine pregnancy testing will be performed at all other visits. Pregnancy tests must be confirmed as negative prior to dosing with study drug. Urine pregnancy test must be completed and confirmed as negative either the day of or the day prior to any PET scan. Refer to drug-specific appendices for OLE collection timing.

NOTE: Post-menarchal, pre-menopausal people who have undergone tubal ligation are required to have pregnancy testing performed as scheduled at treatment visits. In cases where urine collection proves difficult based on a participant's symptom progression, e.g., incontinence, alternative methods for pregnancy testing may be used with prior sponsor approval.

6.1.11 Drug-specific Testing

There will be specific laboratory tests for each study compound (e.g., drug levels for pharmacokinetics [PK] and immunological monitoring for immunotherapy including anti-drug antibodies [ADA]). Frequency and specific visit requirements will be specified in each drug-specific appendix. Refer to the central laboratory manual and the *Global Manual of Operations* for additional details on specific sample collection and processing procedures.

6.1.12 Stored Samples (Blood and DNA)

Selected samples (e.g., plasma, DNA, buffy coats, and CSF cell pellets), will be collected and stored for future use so that testing for as yet undiscovered biomarkers can be performed (including, but not limited to, protein biomarker identification, single-gene or genome-wide analyses, epigenetics, single cell RNA). Stored samples may also be used to address regulatory inquiries or for additional monitoring of anti-drug antibodies or other drug-specific analyses.

Because of future trials platform needs, samples will not be discarded or destroyed unless the DIAN-TU determines there is no use for them, or they can no longer be stored.

Types of samples to be collected, frequency, and specific visit requirements are specified in the drug-specific schedule of visits. Refer to the central laboratory manual for additional details on specific sample collection and processing procedures.

The biomarkers chosen as endpoints for this study were based on currently available data, but new biomarkers are likely to emerge in the coming years. These samples will be used for future studies on the mechanism of action of Alzheimer's treatments and other studies related to neurodegenerative disorders under the supervision of Washington University and the DIAN-TU. These samples will be stored using the participant identification number. Samples will be stored indefinitely unless otherwise specified, and samples will not be discarded or destroyed

unless the DIAN-TU determines there is no use for them or they can no longer be stored. Collection and storage of these samples is mandatory unless prohibited by local laws.

6.1.13 Study Drug Administration

Study drug dosing may be performed at the DIAN-TU site, or for participants who live at a distance from the host DIAN-TU site, dosing may be administered by the trial-designated home health nurses or at other trial-identified locations. Study staff who administer study drugs will have training and supplies necessary to treat allergic reactions including anaphylaxis.

Details of study drug administration or dispensing should be recorded; see *Global Manual of Operations* for details.

Requirements for monitoring participants after study drug administration are detailed in each drug-specific appendix.

For the study drug administration visits following the occurrence of a safety MRI, the site principal investigator or designated sub-investigator must review the MRI central read prior to proceeding with the subsequent dose administration for parenterally administered treatments.

6.1.14 Cognitive Testing

Cognitive batteries administered in the gantenerumab and solanezumab double-blind treatment arms can be found in previous protocol versions. Cognitive testing should be performed early in the day before other invasive or stressful procedures.

6.1.14.1 Gantenerumab OLE Period

The Complete Cognitive Battery will be performed annually at the DIAN-TU site, and a subset of the testing battery (the Cognitive Battery Subset) will be performed approximately every 6 months. See the *Gantenerumab OLE DIAN Trials Unit Cognition Core Procedures Manuals* for additional details and suggested timing for administration of cognitive testing.

All staff administering these batteries must be appropriately trained and certified as specified in the *Gantenerumab OLE DIAN Trials Unit Cognition Core Procedures Manuals*. The following tests will not be administered at any visit to participants who had a CDR of 1 at gantenerumab or solanezumab double-blind baseline (V2) visit: Groton Maze Learning Test, Behavioral Pattern Separation Object Task, and MAC-Q.

Complete Cognitive Battery (annual visits)

Cognitive measures to be obtained at the OLE baseline visit (OLE V1) and annual OLE visits are administered at a DIAN-TU site and include the iPad-administered and conventional cognitive (pen/paper) tests listed below.

iPad-administered Cognitive Testing:

- International Shopping List Test (12-Item Word List Learning): 3 learning trials, Immediate Recall, 30-min Delayed Recall (Cogstate)
- Groton Maze Learning Test*: Timed Chase Task, 5 learning Trials, Immediate Recall, 30-min Delayed/Reversed Recall (Cogstate)
- Cogstate Detection Task
- Cogstate Identification Task
- Cogstate One Card Learning Test
- Cogstate One-Back Task
- Behavioral Pattern Separation Object Task*
- MAC-Q*

Conventional Cognitive Testing (Pen/Paper):

- Trailmaking Test parts A & B
- WMS-R Digit Spatial Span Forward and Backward
- WAIS-R Digit-Symbol Substitution Test
- Raven's Progressive Matrices (Set A)
- Category Fluency (Animals & Vegetables)
- WMS-R Logical Memory/Paragraph Memory (Immediate & Delayed Recall)

*These tests should not be administered at any visit to participants who had a CDR of 1 at their original double-blind period baseline (V2) visit.

Cognitive Battery Subset (every six [6] months when not annual):

The subset of the complete cognitive battery will be administered by the site or trial-certified cognitive rater at the gantenerumab OLE visits occurring at the approximate 6-month treatment visits between annual visits and includes the iPad-administered and conventional cognitive (pen/paper) tests listed below.

Conventional Cognitive Testing (Pen/Paper):

- Trailmaking Test parts A & B
- WMS-R Digit Span
- WAIS-R Digit-Symbol Substitution Test
- WMS-R Logical Memory (Immediate & Delayed Recall)

In addition, the cognitive measures listed below will be administered by the site or trial-certified cognitive rater:

iPad-administered Cognitive Testing

- International Shopping List Test (12-Item Word List Learning): 3 learning trials, Immediate Recall, 30-min Delayed Recall (Cogstate)
- Groton Maze Learning Test: Timed Chase Task, 5 learning Trials, Immediate Recall, 30-min Delayed/Reversed Recall (Cogstate)*

- Cogstate Detection Task
- Cogstate Identification Task
- Cogstate One Card Learning Test
- Cogstate One-Back Task

*These tests should not be administered at any visit to participants who had a CDR of 1 at their original double-blind period baseline (V2) visit.

6.1.14.2 Cognitive Run-In Period and Tau Drug Arms: DIAN-TU Harmonized Cognitive Battery

The DIAN-TU Harmonized Cognitive Battery will be performed approximately every 26 weeks (~6 months) for the CRI secondary prevention population and for tau drug arms; and every 52 weeks (annually) for the CRI primary prevention population by a trial-certified cognitive rater at either the host DIAN-TU site or home health nursing visit.

Cognitive measures to be obtained in the Cognitive Run-In (CRI) and tau-targeted study drug arms include the below listed tests.

DIAN-TU Harmonized Cognitive Battery:

- Memory Complaint Questionnaire (MAC-Q)
- Buschke and Grober Free and Cued Selective Reminding Test-Immediate Recall (FCSRT-IR)
- WMS-R Logical Memory/Paragraph Memory (Immediate & Delayed Recall), Alternate Paragraph for Logical Memory I & II – Version A (Immediate and Delayed) and Alternate Paragraph for Logical Memory I & II – Version B (Immediate and Delayed)
- Category Fluency (Animals)
- WAIS-R Digit-Symbol Substitution Test
- Trailmaking Test Parts A & B
- WMS-R Digit Spatial Span Forward and Backward

IMPORTANT for baseline treatment visit 2 (V2): If the CRI period is open to enrollment, a CRI period may last until a study drug arm opens for randomization, but no longer than approximately 3 years. If a participant is taking part in a CRI period, a minimum of 8 weeks must elapse between the participant's last administration of a cognitive battery during the CRI period and administration of the baseline (V2) cognitive battery.

Smartphone-based Cognitive Assessments

Smartphone-based cognitive (Ambulatory Research in Cognition [ARC]) assessments will be administered to participants using a mobile phone application, developed at Washington University in St. Louis. These tests will include measures of episodic memory, attentional control, and processing speed and are administered multiple times per day over the course of several days. These assessments will be self-administered by the participants on their personal

smartphones. If participants do not own a smartphone or their device does not meet minimum specifications, a study phone will be provided.

Compliance with the smartphone-based cognitive measures is considered exploratory and non-participation will not be considered reason for discontinuation in the study and will not be considered protocol deviations. Based on operational and regulatory considerations, the study sponsor will determine which sites will administer the smartphone-based cognitive assessments, with the explicit goal of full site participation.

Participants will be instructed on installation and setup of the ARC application at their CRI screening visit (CRI Screen) or drug arm screening visit (V1). Participants will complete the first week of assessments immediately following the CRI screening visit or screening visit (V1) of a treatment arm. Participants will continue to complete assessments approximately every 26 weeks (approximately 6 months) for the secondary prevention population and every 52 weeks (annually) for the primary prevention population after the CRI entry visit (CRI Entry) and/or baseline (V2) of a treatment arm.

6.1.15 Baseline and Annual Magnetic Resonance Imaging (MRI)

For all drug arms, MRIs performed at the DIAN-TU site at annual visits starting with CRI Entry and/or baseline [V2] visits, will include structural and functional MRI and other additional MRI endpoints in addition to sequences for safety monitoring. All MRIs, including safety MRI scans performed off site, if applicable (see Section 6.1.16), will utilize standardized sequences that include fluid-attenuation inversion recovery (FLAIR) and T2*-weighted gradient-recalled-echo (GRE) sequences. Additional scheduled safety MRI assessments between annual visits may be scheduled based on study drug arm (see each drug-specific appendix).

MRIs use a standardized protocol specified by the DIAN-TU Imaging Core (see *MRI Technical Manual* for specific sequences). The DIAN-SHORT protocol, a core set of MR sequences necessary for safety MR and PET processing, will be used for off-site MRIs and may be used at the host site for those whom, in the estimation of the site principal investigator, would not be able to complete the full-length protocol (e.g., participants who are unable to remain still for the full MR session, approximately 45 minutes in duration). MRI should be performed before lumbar puncture (if on the same day) or scheduled to be on a different day than the lumbar puncture.

Scanners will be evaluated and qualified by the Mayo-ADIR Clinic prior to participant scanning, and ongoing quality control of the MRI scans will be performed at the Mayo-ADIR Clinic.

MRIs will be uploaded to the trial-designated imaging data management system (DIAN Central Archive [DCA]).

Images should be uploaded within 24 to 48 hours of scan completion; failure to upload the images within 3 working days of receipt of the images will be considered a protocol deviation.

Images from the CRI Entry, CRI annual visits, baseline MRI (V2), and all annual visit MRIs should be uploaded immediately after these scans are completed as the findings of these MRIs

can impact inclusion in the study (CRI Entry and baseline [V2] MRI) and thereafter alter dispensing/administration of next dose(s) of study drug.

Volumetric analysis of the baseline and the annual MRIs will be performed by Washington University and will include measures of hippocampal volume, ventricular volume and whole brain volume. Site investigators will not receive results of the volumetric analysis. All MRI scans will be analyzed for amyloid-related imaging abnormalities (ARIA) and for incidental findings at the Mayo-ADIR Clinic; this includes safety MRIs (see Section 6.1.16). Findings on the baseline MRI will determine eligibility; therefore, results of the baseline read will be made available before randomization and first dispensing/administering of study drug. ARIA findings during the study may result in a change or halting of study drug dosing; see each drug-specific appendix for additional information. See *Global Manual of Operations* for additional details and *MRI Technical Manual* for technical information.

Additional MRI examinations for the OLE period will be listed in the drug-specific appendices.

6.1.16 Safety Magnetic Resonance Imaging (MRI)

Safety MRIs on 3T scanners will be done primarily to monitor for ARIA. Safety MRIs may be done at the host DIAN-TU site or, for participants who live at a distance from the host DIAN-TU site, at a site closer to the participant's home in order to reduce participant travel burden. When not performed at the DIAN-TU site, safety MRIs may be performed at an ADNI/ADCS site if possible or at a 3T scanner near the participant's home. Local centers not previously qualified as a DIAN, ADCS or ADNI-equivalent site will be pre-qualified for the DIAN-TU trial protocol by the Mayo-ADIR Clinic. With the exception of the MRIs done at the DIAN-TU site during annual visits, safety MRIs should be performed on the same scanner throughout the trial.

Standardized sequences will be used for these scans and will include fluid-attenuation inversion recovery (FLAIR) and T2*-weighted gradient-recalled-echo (GRE) sequences. See *MRI Technical Manual* for additional information. Sites must ensure that study visits are scheduled so that MRI images are uploaded and available for central read at least 3 to 5 working days before next administration of study drug for parenterally administered drugs.

A central read for safety purposes (e.g., analysis of ARIA) will be completed at the Mayo-ADIR Clinic within 1 week (5 working days) of upload for routine exams; and within 24 hours for the MRIs done for all drug arms at CRI Entry, and treatment period baseline (V2), and annual visits preceding dose administration.

A central read for safety purposes may also be completed for annual OLE visits and routine exams as specified in the drug-specific appendices.

The central read results will be communicated to site principal investigators (site PIs) or designated sub-investigator, Project Arm Leader (PAL), and Medical Director or designee. This communication will occur at least one week before the next scheduled drug dispensing/administration. Extent of ARIA-E and presence of definite and possible ARIA-H changes will be reported; reports including significant or new definite findings will be flagged

for review by site principal investigator or designated sub-investigator, PAL, and sponsor Medical Director or designee. The site principal investigator or designated sub-investigator will review the findings and drug-specific guidelines for dosing adjustment (see each drug-specific appendix) with the PAL. The PAL will confer with the Medical Director or designee who has final authority on dose adjustment decisions (e.g., extra study visit, repeat or more frequent safety MRIs, suspension of study drug administration or dose adjustment; see each drug-specific appendix for discussion of ARIA-related interventions). The Medical Director has the final decision on whether a dose is released for treatment. See *Global Manual of Operations* for further details on communication between the site principal investigator or designated sub-investigator, PAL, and Medical Director or designee. See *MRI Technical Manual* for technical information.

When an imaging visit precedes a visit where study drug is parenterally administered, it is the responsibility of the DIAN-TU site principal investigator or designated sub-investigator to review the central read safety MRI results before study drug administration and communicate any changes in study drug administration to the site staff or home health nurse preparing and administering the study drug.

Local read for safety MRIs is not required for purposes of this study but should be performed if needed in accordance with local requirements. Should a local read be obtained and be different from the central read, central read has priority for study purposes.

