- ^b Sentinel safety cohort. The first 20 participants to complete the first two doses at CCI and CCI must complete a safety MRI after two doses at each dose level as part of the sentinel safety cohort before additional participants may dose titrate to that dose level. Safety MRI data will be reviewed and cleared before additional participants will be allowed to up-titrate to each of the higher dose levels.
- ^c A safety MRI will be scheduled 1 week (\pm 4 days) after the sixth dose of each CCI titration step CCI CCI unless otherwise indicated by the ARIA-E and ARIA-H management algorithms (Section 1.14). If an annual visit follows the third dose of a titration step, the annual MRI assessment can fulfill this requirement as long as the MRI reading is reviewed prior to dosing at that visit.
- ^d Once at stable dose of CCI, safety MRIs will be scheduled 1 week (\pm 4 days) after every 12th dose (or approximately every 6 months) for the remainder of the trial unless otherwise indicated by the ARIA-E and ARIA-H management algorithms (Section 1.14).
- ^e The titration schema was designed to reach the target dose of CCI; however, the target dose may not be achieved as otherwise dictated by ARIA-E and ARIA-H management algorithms (Section 1.14) or more conservative action by the site principal investigator/DIAN-TU Medical Monitors. Once a participant reaches their stable dose (defined as the maximum dose the participant will remain at for the duration of the trial) safety MRIs will follow every 12 doses (or approximately every 6 months) unless otherwise indicated by the algorithm.

NOTE: The annual/volumetric MRI assessment can fulfill the safety MRI assessment as long as the MRI reading is reviewed prior to dosing at that visit.

Participants should receive at least C doses at each titration step CCI CCI weeks (\pm 4 days) apart, and C doses at CCI CCI 2 weeks (\pm 3 days) apart, before proceeding to the next titration step (Table 5). The titration schema was designed to reach the target dose of CCI administered every CCI; however, the target dose may not be

achieved as otherwise dictated by the ARIA-E and ARIA-H management algorithms (Section 1.14) or more conservative action by the site principal investigator/DIAN-TU Medical Monitors.

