3.2.9.1 Regular Safety MRIs

Timing: Annual MRIs in addition to Weeks 9, 21 and 33 weeks \pm 4 days from OLE V1 (calculated from the day of the first dose) during Q4W dosing; and Weeks 59, 71, 83, 95, and 127 weeks \pm 3 days from OLE V1 (calculated from the day of the first dose) during Q2W dosing as outlined in Figure 1 and Table 5 in this appendix. Sites must ensure that study visits are scheduled so that MRIs are uploaded and available for central read at least 5 working days before next administration of study product.

Note: Based on when amendment 11 is approved at each site, some participants may commence dose titration above CCI after having more than 3 doses at that dose level. In these cases, the medical monitoring team will review the participant's current visit schedule to identify the timing of the MRIs in the same manner as outlined in the schedule of visits however, the exact visit numbers may not align.

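### At Q2W dosing the OLE safety MRI is nominally 7 days before the next dose, so the one-week notice rule leaves no time for upload or central read

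*Protocol*

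**What the plan says.** Main protocol 6.1.16 sets three timing rules for safety MRIs:

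- Availability: images are to be "uploaded and available for central read at least 3 to 5 working days before next administration of study drug".
- Read: the central read is due "within 1 week (5 working days) of upload for routine exams". A 24-hour read is given only for CRI Entry, baseline (V2) and annual visits preceding dosing.
- Notice: "This communication will occur at least one week before the next scheduled drug dispensing/administration".

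Main protocol 6.1.15 gives the upload time: "Images should be uploaded within 24 to 48 hours of scan completion". It adds that "failure to upload the images within 3 working days of receipt of the images will be considered a protocol deviation".

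Appendix 3 (gantenerumab) refers to 6.1.16 for safety MRI procedures (3.2.9) and adds its own rules:

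- Under 3.2.9.1, visits are to be scheduled so that "MRIs are uploaded and available for central read at least 5 working days before next administration of study product". The Q2W scans are at weeks 59, 71, 83, 95 and 127, with a window of ±3 days.
- The Table 5 footnotes in 2.2 place the titration scan 1 week (±4 days) "after the sixth dose of each" Q2W titration step. Footnote 14 of the OLE schedule of visits repeats the ±4 days.
- Under 1.13.1, the decision on new ARIA must reach the site within 7 days of the report, and at the latest on the day before the next dose.

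**The concern.** A scan one week after a dose, on a two-week cycle, is also one week before the next dose. If the result must be known a week ahead of that dose, it is due on the day of the scan. The rules appear to have been written for longer dosing intervals and carried over when the OLE moved to Q2W.

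This matters because review of the central read gates the next dose (main protocol 6.1.13 and 6.1.16; Appendix 3, 1.5.2.1). The week-59 scan precedes the week-60 step to the last dose level. A site following the nominal calendar must either miss a stated safety-communication rule or move the scan or the dose. The protocol does not tell sites which rule yields.

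**Working it through.** **1. Reproduce the plan's scan weeks.** Q2W doses start at week 48 and run 48, 50, 52 and so on.

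- Sixth dose of the first block: 48 + 2×5 = 58; one week later is week 59.
- The next blocks of six end at weeks 70, 82 and 94, giving scans at 71, 83 and 95.
- Twelfth dose counted from week 104: 104 + 2×11 = 126; one week later is week 127.

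All five agree with Appendix 3, 3.2.9.1. Doses at weeks 48 to 58 are the six at the first Q2W level, so week 60 starts the last level. The sentinel scans follow the second dose at each level (weeks 50 and 62), giving weeks 51 and 63, as in footnote 19 of the schedule.

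**2. Time available from scan to next dose.** The visit tables put the next doses at weeks 60, 72, 84, 96 and 128.

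- Nominal: 14 − 7 = 7 days.
- With windows, the gap is (14 ± 3) − (7 ± w) days:
  - w = 3 (section 3.2.9.1): 1 to 13 days.
  - w = 4 (Table 5 footnotes and schedule footnote 14): 0 to 14 days.

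**3. Time needed = upload + read + 7 days' notice.** Scans are taken on Monday to Friday and the read is counted in working days.

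| Upload | Read | Days from scan to dose |
|---|---|---|
| 24 hours | immediate | 8 |
| same day | 1 working day | 8 to 10 |
| 24 hours | 5 working days | 14 to 15 |
| 48 hours | 5 working days | 14 to 16 |
| 3 working days (deviation limit) | 5 working days | 17 to 19 |

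No row fits the nominal 7 days. With full allowances, the 14-day figure arises only for a Friday scan. It fits only at both extremes of the ±4-day rule: scan 4 days early and dose 3 days late. It does not fit the ±3-day rule.

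**4. What does fit.** A scan 3 days early with the dose on its nominal day leaves 14 − 4 = 10 days, so 10 − 7 = 3 days for upload and read. If the dose is also 3 days late, the gap is 13 days, leaving 6.

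**5. The appendix's availability rule at nominal timing.** With the dose 7 days after the scan, images uploaded at 24 to 48 hours are in place 3 to 4 working days before the dose for Monday to Thursday scans, and 5 for Friday scans. The 5-working-day rule is therefore usually missed unless upload is on the same day.

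**6. Availability against the decision deadline.** Images arriving exactly 5 working days before the dose, followed by a full 5-working-day read, give a result on the dosing day. Appendix 3, 1.13.1 needs the decision on new ARIA by the day before.

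**7. Q4W for comparison.** The scan is one week after a dose on a 28-day cycle, so the nominal gap is 28 − 7 = 21 days. The 14 to 16 days fit. At nominal timing the problem is specific to Q2W.

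**The case against.** The strongest reply is that upload and read times are upper limits and only the notice is a minimum. A quick upload and read break no rule, and the windows give room for them. That stands. A reader might infer that the rules need more than two weeks and so cannot be met at Q2W. The documents do not support this: 14 to 16 days is what the allowances permit, and step 4 shows compliant schedules.

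Other replies also have force:

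- Three to five working days in the main protocol and five in the appendix may look contradictory. They are not, because meeting the stricter appendix rule meets both.
- The sentinel scans have the same nominal spacing, but Appendix 3, 3.2.9.2 gives no upload or read time for them. Treating them as routine exams would be inference.
- A reader might infer that participants would be dosed without a read. The gating rules say otherwise, and Appendix 3, 1.13.1 stops further dosing after new ARIA until review is complete. It also lets the MRI schedule be changed for an individual.
- Some detail is deferred to manuals, and Figure 1 and much of Table 5 cannot be read here.

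The appendix could also be said to contain its own workable timeline: images 5 working days before the dose and a decision by the day before. This does not rescue the nominal calendar. Steps 5 and 6 show that the first rule is usually missed after a 24 to 48 hour upload, and that a full-length read starting at that limit ends too late for the second. The legible appendix text neither waives the one-week notice nor sets a faster read for these scans.

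**Conclusion.** The point holds as a scheduling inconsistency. At nominal Q2W timing the one-week notice consumes the whole 7-day gap, so it cannot be met after any upload and read time. With full allowances, 14 to 16 days are needed against at most 13 (±3-day scan window) or 14 (±4-day). Compliance depends on an early scan, a late dose or both, and, outside the one extreme case in step 3, on a read faster than the protocol allows for.

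The expected consequence is missed notice or delayed doses, including at week 60. The SAP's version history records that the OLE ended early, which limits the practical effect for this arm. Section 6.1.16 remains platform text for parenteral drugs.

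Assumptions: regular OLE safety scans are routine exams under 6.1.16; one week is 7 calendar days; there are no holidays; and the upload time in 6.1.15, whose heading is baseline and annual MRI, also covers these scans, since 6.1.16 states none of its own. Dropping the last assumption does not change the nominal result, because the notice alone uses all 7 days.

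**What to change.** The sponsor should reconcile main protocol 6.1.15 and 6.1.16 with Appendix 3 sections 1.13.1, 2.2 (Table 5 footnotes) and 3.2.9.1 and footnote 14 of the OLE schedule. The scan window, upload time, read turnaround, notice and decision deadline should all be achievable on the Q2W calendar, with a single scan window stated. The text should also say which read turnaround applies to the sentinel scans. No particular timing, dose or clinical rule is proposed here.

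The cost is a wording change agreed with the central reader. It needs no new data and no change to the analysis.
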